1.26 Analysis plan

A complete description of the statistical analyses will be specified in a statistical analyses plan, finalised prior to completion of the study.

All analyses will be conducted on an intention-to-treat basis.

The primary analyses will be unadjusted analyses in which binary outcomes will be compared using relative risks with 95% confidence intervals and chi square tests and continuous outcomes will be compared with the use of mean differences and unpaired T-tests assuming that normality assumptions are met. If normality assumptions are not met then we plan to attempt simple data transformation, such as a logarithm transformation, and if this fails to proceed to a Mann-Whitney rank based test. Adjusted analyses will be performed using Poisson regression for binary

FLUid intervention and **Renal Outcome Trial** in patients undergoing major surgery: an observational single-centred study (**FLURO TRIAL**). Version 2, 31st Mar 2014

outcomes and linear regression for continuous outcomes. Baseline covariates will include age, gender, elective vs. emergency surgery, surgical specialty of admission, type of operation, and baseline serum creatinine level. Survival times will be compared using log-rank tests and presented as Kaplan-Meier curves. Multivariable models will be developed to study the predictors of AKI and the independent association between fluid choice and renal outcomes.

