Statistical Methods:	
Primary analyses: will be unadjusted analyses in which binary outcomes will be compared using relative risks with 95% confidence intervals and chi square tests and continuous outcomes will be compared with the use of mean differences and unpaired T-tests assuming that normality assumptions are met.
 
A complete description of the statistical analyses will be specified in a statistical analyses plan, finalised prior to completion of all data collection.
 
If normality assumptions data transformation will be attempted, such as a logarithm transformation, and if this fails to proceed to a Mann-Whitney rank based test.
 
Adjusted analyses: will be performed using Poisson regression for binary outcomes and linear regression for continuous outcomes. Baseline covariates will include age, gender, elective vs. emergency surgery, surgical specialty of admission, type of operation, and baseline serum creatinine level.
 
Multivariable models will be developed to study the predictors of AKI and the independent association between fluid choice and renal outcomes.

Subgroups:	
Patients undergoing abdominal surgery Patients undergoing vascular surgery Patients undergoing thoracic surgery Patients undergoing other major surgeries (orthopaedics, urology etc.) Patients undergoing emergency surgery.

ABBREVIATIONS

IV	Intravenous
CPB	Cardiopulmonary bypass
ECGs	Electrocardiographs
ICU	Intensive Care Unit
APACHE	Acute Physiology and Chronic Health Evaluation

LAY SUMMARY

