1.6 Study design

This study aims to observe the association between perioperative intravenous fluids have and renal function in adult patients undergoing major surgery. **It is a single-centered, prospective observational study and therefore does not change the standard of care in any way.** All patients undergoing surgery at Austin Hospital will be given the perioperative fluids at discretion of the treating clinicians.

The study will be conducted over a 12-week period, allowing a wide variety of amount and type of fluids given to the patients. Austin Hospital staff specialists in anaesthesia agree that on the basis of current evidence, Saline (0.9%), Plasmalyte or Hartmann's solution are equally acceptable for crystalloid fluid therapy in every situation requiring major surgery with the exclusion of surgery for liver transplantation where specific hospital perioperative fluid protocols are used in these settings.

As there is no departure from standard care for this study, Saline (0.9%), Plasmalyte and Hartmann's solution will be available for administration to all patients undergoing major surgery. In the situations, where, in the opinion of the treating anaesthetist or clinician, there is a clinical indication for other types of fluid e.g. colloids, blood, dextrose etc, again there will be no deviation from standard care in any way.

All adult patients who undergo major surgery will be analysed. The primary outcome will be the proportion of patients with kidney injury or failure based on established criteria⁵. Secondary outcomes will include delta creatinine (the difference between baseline and peak creatinine), serum electrolyte levels, acid base disturbances, requirements for ICU, duration of ICU stay, hospital length of stay, complications and in-hospital mortality.

All of the data required for this study are collected routinely as part of standard clinical care and/or quality assurance activities⁶.

FLUid intervention and **Renal Outcome Trial** in patients undergoing major surgery: an observational single-centred study (**FLURO TRIAL**). Version 2, 31st Mar 2014

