1.10 Summary

This is an observational study; there is no departure from standard care at any stage. It involves the collection of data that has already been collected for clinical or quality assurance purposes.

In this study we will be collecting information about intravenous fluid intervention (type of fluid and amount) for adult patients undergoing major surgery (duration >2 hours and at least one overnight stay). Data will be collected over a 12-week period. Specifically, the association of these fluids with kidney function will be investigated. Perioperative care and fluid intervention therefore will remain completely at the discretion of the treating clinicians.

The current study will inform clinicians looking after patients undergoing major surgery about the effects of these fluids on renal injury.

This study will be also be used in Fulfilment of University of Melbourne BSc Honours Project for [name].

FLUid intervention and **Renal Outcome Trial** in patients undergoing major surgery: an observational single-centred study (**FLURO TRIAL**). Version 2, 31st Mar 2014

OBJECTIVES

The overall objective of this study is to determine the association between perioperative intravenous fluids and renal function in adult patients undergoing major surgery.

The choice of perioperative intravenous fluid intervention such as Saline (0.9%) vs. Plasmalyte vs. Hartmann's solution will be entirely at the discretion of the all clinicians caring for the patients.

Specifically, we aim to establish the association of Saline (0.9%), Plasmalyte and Hartmann's solution on:

1. The development of acute kidney injury in hospital
2. The development of biochemical and acid-base derangements
3. The development of postoperative complications
4. Requirements for ICU
5. Requirement for dialysis or hemofiltration
6. Duration of ICU stay
7. Hospital length of stay
8. Hospital mortality

STUDY DESIGN

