1.16 Study treatments

This is not an interventional study. This is an observational study only. Therefore, there is no departure from standard care at any stage. It only involves the collection of data that has already been collected for clinical or quality assurance purposes. Perioperative care and fluid intervention will remain completely at the discretion of the treating clinicians.

[figure not shown]

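### The primary AKI analysis is an unadjusted relative risk although clinicians choose the fluid, so the headline estimate is exposed to confounding by indication while the planned adjusted model is not ranked first

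*Protocol*

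**What the plan says.** The primary analysis is fixed in two places. Section 1.26 has: "The primary analyses will be unadjusted analyses in which binary outcomes will be compared using relative risks", tested by chi-square. The synopsis, under Statistical Methods, has: "Primary analyses: will be unadjusted analyses in which binary outcomes will be compared using relative risks with 95% confidence intervals".

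Exposure is not assigned by the study. Section 1.6 says patients "will be given the perioperative fluids at discretion of the treating clinicians". Section 1.16 has: "Perioperative care and fluid intervention will remain completely at the discretion of the treating clinicians". Under Objectives, the choice between saline, Plasmalyte and Hartmann's "will be entirely at the discretion of the all clinicians caring for the patients". Sections 1.17 and 1.28 mark allocation and randomisation as not applicable. The inclusion criteria admit elective and emergency surgery of any specialty, with liver transplantation excluded.

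Adjusted analyses are also planned. They "will be performed using Poisson regression for binary outcomes and linear regression for continuous outcomes", with age, gender, urgency, surgical specialty, type of operation and baseline creatinine as covariates. Section 1.26 leaves the independent role of fluid choice to multivariable models. None of these is named as primary.

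**The concern.** In an unrandomised cohort, a crude RR combines any effect of the fluid with the reasons for choosing it. The protocol's own background gives such reasons. It reports advice to avoid Hartmann's in liver resection, and it notes that Plasmalyte is compatible with citrated blood products. If the groups differ in urgency, operation or baseline renal function, the crude comparison can show a difference that the fluid did not cause, or hide one that it did.

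This matters because of the intended use. Section 1.10 says the study will tell clinicians about the fluids' effects on renal injury. Section 1.7 calls it preliminary efficacy evidence for a larger interventional study, and the Background expects it to supply outcome data for power calculations. The ranking of the analyses decides which number is the headline and which one governs if crude and adjusted results disagree.

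**Working it through.** **Planning effect.** Section 1.25 gives 14% and 8.4%, so RR = 0.14/0.084 = 1.67 for the chloride-liberal side, or 0.60 the other way. This is the yardstick below. The power claim in 1.25 is a separate matter and is not used here.

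**Illustration: imbalance in urgency only, no fluid effect.** All four inputs are assumptions, because the protocol gives none of them: 25% emergencies; AKI 20% in emergency and 8% in elective cases; saline in 50% of emergencies and 25% of elective cases.

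- Saline group: 0.25×0.50 + 0.75×0.25 = 0.125 + 0.1875 = 0.3125 of the cohort. Emergency share 0.125/0.3125 = 40%.
- Others: 0.125 + 0.5625 = 0.6875. Emergency share 0.125/0.6875 = 18.2%.
- AKI, saline: 0.40×0.20 + 0.60×0.08 = 0.128.
- AKI, others: 0.182×0.20 + 0.818×0.08 = 0.102.
- Crude RR = 0.128/0.102 = 1.26 (1.257 unrounded). The RR within each urgency stratum is 1.

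**Direction.** Swap the assumed saline use (25% of emergencies, 50% of elective cases).

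- Saline group: 0.0625 + 0.375 = 0.4375 of the cohort, 14.3% emergency, AKI 0.143×0.20 + 0.857×0.08 = 0.097.
- Others: 0.1875 + 0.375 = 0.5625, 33.3% emergency, AKI 0.333×0.20 + 0.667×0.08 = 0.120.
- Crude RR = 0.097/0.120 = 0.81. The bias can go either way.

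**Range.** For one binary confounder that multiplies risk by R, with prevalence pS in saline patients and pO in the others, and a true fluid RR of 1:

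crude RR = [1 + pS(R−1)] / [1 + pO(R−1)]

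Assume pO = 20%:

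| pS | R = 1.5 | R = 2 | R = 3 |
|---|---|---|---|
| 30% | 1.05 | 1.08 | 1.14 |
| 40% | 1.09 | 1.17 | 1.29 |
| 50% | 1.14 | 1.25 | 1.43 |
| 60% | 1.18 | 1.33 | 1.57 |

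**False rejections of a true null.** Assume N = 600 split 1:1 and average AKI (14 + 8.4)/2 = 11.2%. For R = 3 and 40% vs 20% emergencies, group risks are 12.6% and 9.8%. The pooled SE is √(2×0.112×0.888/300) = 0.0257, so z = 0.028/0.0257 = 1.09. The two-sided test rejects about 19% of the time at 0.05 and 7% at 0.01. For 50% vs 20% (13.2% and 9.2%) the figures are about 33% and 15%. For R = 2 and 40% vs 20% (12.1% and 10.3%) they are about 10% and 3%.

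**What the adjusted model can carry.** At 11.2%, expected events are 400×0.112 = 45 to 600×0.112 = 67. A two-level fluid term plus linear age, gender, urgency and linear creatinine make five parameters, or 45/5 = 9 to 67/5 = 13 events each. That is before any specialty or operation category is added.

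**The case against.** *The research question asks only about association, and a crude RR estimates one.* True, and a reader who infers that the crude RR fails to answer the stated question goes too far. The point rests instead on the effects, efficacy and trial-design uses in 1.7, 1.10 and the Background, for which a crude association is not enough.

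*Section 1.6 says the hospital's specialists regard the three crystalloids as interchangeable for all major surgery except liver transplantation, which is excluded.* This is the best defence, and it means that bias cannot be taken as certain. But an opinion about equipoise does not make the choice in each patient independent of prognosis, and the Background gives operation- and patient-linked reasons to choose.

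*The adjusted results will be reported anyway, and 1.27 has an emergency-surgery subgroup.* Correct, so the fault is one of ranking and not of missing analyses.

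*The SAP can settle it.* It may add detail, but the protocol does not leave the choice of primary analysis open. It states it twice.

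Two further readings are tempting but unsupported. One is that an RR with a chi-square test belongs only to randomised trials. Both are ordinary cohort methods, and the problem is the absence of adjustment. The other is that Poisson regression for binary outcomes gives wrong standard errors here. The protocol does not say which variance estimator will be used, and that is a usual SAP detail. Model-based errors would in any case be conservative: the SE ratio is √[(1/0.14 + 1/0.084)/(0.86/0.14 + 0.916/0.084)] = 1.06, about 6% too large at the planning rates.

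**Conclusion.** The point holds as a fault in which analysis is ranked primary. The protocol fixes an unadjusted RR as the headline for a clinician-chosen exposure in a mixed elective and emergency cohort, and leaves the adjusted estimate without primary status. Under the assumed imbalance in urgency, the crude RR is about 1.26 with no fluid effect. Across the other assumed imbalances it runs from 1.05 to 1.57, and it falls below 1 if the imbalance is reversed. The planning RR is 1.67, so confounding by one listed covariate could account for a material part of the effect sought.

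A reader might infer that the study's result will be biased, or biased by these amounts. The documents do not support that. They give no emergency share, no AKI rate by urgency and no pattern of fluid use, so the figures show only what is possible.

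**What to change.** In the synopsis and in 1.26, name the covariate-adjusted RR for AKI as the primary analysis and the unadjusted RR as descriptive. Fix the covariates before analysis: age, gender, urgency, specialty, operation type and baseline creatinine. Specialty and operation type overlap and have many categories, so collapse them in advance into a few groups that about 45 to 67 events can support. That count uses the 1.25 rates, which come from critically ill patients classed by RIFLE injury and failure, so it should be revisited once the number of events in this cohort is known.

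The cost is low: two analyses already planned change places, and no new data are needed. Two downsides should be stated in the protocol. The headline result will depend on the covariate model, with some risk of sparse cells. Residual confounding will also remain, because section 1.15 collects comorbidity and illness severity only for patients admitted to ICU and neither is in the covariate list.

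Stating a robust variance for the Poisson model would be a useful clarification, but it is optional and not part of this point.

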Potassium (K ⁺), meq/L	4.0 (3.5 to 5.0)	5	0	0
Calcium (Ca ²⁺), meq/L	2.4 (2.3 to 2.6)	0	0	0
Magnesium (Mg ²⁺), meq/L	2.0 (1.4 to 2.4)	3.0	0	0
Acetate, meq/L	0	27	0	0
Gluconate meq/L	0	23	0	0
Lactate, meq/L	1.0 (0.5 to 2.0)	0	0	0
Strong Ion Difference meq/L	44	49	0	0

*All fluids are manufactured by Baxter Healthcare, Toongabie, NSW.

**Median, Reference Range

FEASIBILITY AT AUSTIN HOSPITAL

The departments of Anaesthesia and Intensive Care at Austin Hospital have completed 6 fluid intervention studies, and currently there is one fluid intervention study still underway in the setting of renal transplantation.

Fluid intervention in liver resection

Recently, the authors completed a multicentre randomized double-blind controlled multicentre study of Plasmalyte vs. Hartmann's solution in patients receiving liver resection³². Participants were randomized to Plasmalyte or Hartmann's solution for intraoperative fluid intervention. Primary outcome: base-excess immediately after surgery. Secondary outcomes: lactate levels, strong-ion-difference (SID), total weak acids, net-unmeasured-ions, changes in liver enzymes, perioperative complications and duration of hospital stay.

Results: 60 participants were recruited from 4 tertiary-level hospitals. Both groups were matched according to baseline characteristics, extent of resection, and surgery duration. There were no differences in the volume of trial fluid used, perioperative fluid balance, or urine output. Plasmalyte was not inferior to Hartmann's for the

FLUid intervention and **Renal Outcome Trial** in patients undergoing major surgery: an observational single-centred study (**FLURO TRIAL**). Version 2, 31st Mar 2014

primary endpoint. Plasmalyte base-excess was 0.8mmol/L greater (95%CI: -0.4 to 2.0;P=0.18). This was associated with hyperchloraemia (Difference 1.7mmol/L, 95%CI: 0.2 to 3.2mmol/L, p=0.03) and hyperlactaemia (Difference 0.8mmol/L, 95%CI: 0.2 to 1.3mmol/L; P=0.01) in the Hartmann's group. In the Hartmann's group 23 patients (77%) had a lactate above the reference range compared to 14 patients (47%) in the Plasmalyte group, P=0.02. Complications were more frequent in the Hartmann's Group (56% vs. 20%, 95%CI: 1.3 to 6.1;P=0.007). Median length of hospital stay: 5.9 days vs. 7.8 days (P=0.041) favouring Plasmalyte group.

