1.25 Power calculations and sample size

A recently published open label sequential period study of chloride-liberal vs. chloride-restrictive fluid administration² demonstrated a reduction in the incidence of injury and failure based on RIFLE criteria from 14% (95% CI, 11% - 16%) to 8.4% (95% CI, 6.4% - 10%); $P < 0.001$) with the introduction of a chloride-restrictive fluid regime.

Assuming that, as we have conservatively estimated, we can study 400-600 subjects over a 6-week period, our sample size will provide more than 90% power with an alpha of 0.01 to detect a difference of this magnitude between patients treated with saline vs. patients treated with different crystalloid fluids.

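### The adjusted analyses of binary outcomes name Poisson regression without a robust variance; with model-based standard errors their intervals would be too wide, slightly for AKI and materially for common outcomes

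*Protocol*

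**What the plan says.** Section 1.26 (Analysis plan) sets two layers of analysis for binary outcomes.

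- **Primary, unadjusted:** "The primary analyses will be unadjusted analyses in which binary outcomes will be compared using relative risks with 95% confidence intervals", together with chi-square tests.
- **Adjusted:** "Adjusted analyses will be performed using Poisson regression for binary" outcomes, with age, gender, urgency, specialty, type of operation and baseline creatinine as covariates.

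The Statistical Methods row of the synopsis repeats that adjusted analyses "will be performed using Poisson regression for binary outcomes and linear regression for continuous outcomes". Neither place says how the standard errors of the Poisson model are to be obtained. The terms robust, sandwich, modified Poisson and log-binomial do not occur, and neither do ordinary, default or model-based.

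Section 1.26 also defers detail: "A complete description of the statistical analyses will be specified in a statistical analyses plan, finalised prior to completion of the study". That plan was not available for this review.

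**The concern.** Poisson regression with a log link is a sensible way to obtain an adjusted relative risk, and its point estimate is sound for a 0/1 outcome. Its own variance formula is not. The Poisson likelihood takes the variance to equal the mean, p, whereas a binary outcome has variance p(1-p). The model-based SE is too large, and increasingly so as the outcome becomes more common.

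This matters here because clinicians choose the fluid, so the unadjusted comparison is open to confounding by indication. The adjusted models are the ones meant to isolate the independent association of fluid choice with outcome. The conventional unadjusted relative-risk interval and the chi-square test in the same section use the binomial variance. If the adjusted model does not, an interval can widen on adjustment only because the variance formula changed. A finding that loses significance in this way could be misread as explained by confounding. The study is also meant to supply preliminary outcome data for later power calculations, so the width of its intervals has a direct use.

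**Working it through.** The protocol gives no figure for the precision of the adjusted model. Its power statement in section 1.25 is not an input to this check.

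**Inputs**
- AKI risks 14% and 8.4%: section 1.25, from the cited chloride study.
- Complication risks 56% and 20%: the liver-resection trial under Feasibility. Using them for this cohort is an assumption.
- Total sample 400 to 600: section 1.25. Equal groups are assumed.
- Risk of 2% for a rare outcome such as death: assumed.

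**Formulas** for the SE of the log relative risk with two groups
- Model-based Poisson: sqrt[1/(n1·p1) + 1/(n0·p0)]
- Binomial: sqrt[(1-p1)/(n1·p1) + (1-p0)/(n0·p0)]
- With a common risk p the ratio is 1/sqrt(1-p), whatever the sample size.
- Actual two-sided level of a nominal 0.05 test: 2·[1 - Φ(1.96 × ratio)]

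**Step 1: an interval printed in the protocol.** For the liver-resection trial the protocol reports: "Complications were more frequent in the Hartmann's Group (56% vs. 20%, 95%CI: 1.3 to 6.1;P=0.007". The trial had 60 patients, and its counts of 23 (77%) and 14 (47%) imply 30 per group. The relative risk is 0.56/0.20 = 2.8.
- Binomial SE = sqrt(0.44/16.8 + 0.80/6) = 0.399, giving 1.28 to 6.13. This matches the printed 1.3 to 6.1.
- Poisson SE = sqrt(1/16.8 + 1/6) = 0.476, giving 1.10 to 7.11.

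The same data under the Poisson variance give an SE 19% larger (ratio 1.19) and a visibly wider interval.

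**Step 2: AKI, 200 per group.**
- Poisson: sqrt(1/28 + 1/16.8) = 0.3086
- Binomial: sqrt(0.86/28 + 0.916/16.8) = 0.2920
- Ratio 1.057, coverage about 96.2%, actual level about 0.038. At 300 per group the ratio is the same (0.2520/0.2384).

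**Step 3: across outcome frequencies**, common risk in both groups.

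| Risk | SE ratio | Actual level for nominal 0.05 |
|---|---|---|
| 2% (assumed) | 1.01 | 0.048 |
| 11.2% (midpoint of 8.4% and 14%) | 1.06 | 0.038 |
| 20% | 1.12 | 0.028 |
| 38% (midpoint of 20% and 56%) | 1.27 | 0.013 |
| 56% | 1.51 | 0.003 |

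**Step 4: does this carry over to a covariate-adjusted model?** Poisson regressions were simulated with no fluid effect, one continuous and one binary covariate, 500 patients and 2,000 runs.

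| Risk | Type I error, model-based | Type I error, robust | Mean SE ratio |
|---|---|---|---|
| about 11% | 4.4% | 5.7% | 1.07 |
| about 38% | 1.2% | 5.5% | 1.30 |

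The simulation error near 5% is sqrt(0.05 × 0.95/2000), about 0.5 percentage points, so the robust results agree with the nominal level.

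**Step 5: power, 250 per group, nominal 0.05.** Power with the binomial SE is Φ(log RR/SE_bin - 1.96). With the Poisson SE it is Φ[(log RR - 1.96·SE_Poi)/SE_bin].
- AKI 14% vs 8.4%: log RR 0.511, SEs 0.2611 and 0.2760; power 50% falls to 45%.
- Illustrative 43% vs 33% (not a protocol figure): log RR 0.265, SEs 0.1159 and 0.1464; power 63% falls to 42%.

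**The case against.** The strongest reply is that the protocol does not make the mistake. It names a model family, not a variance estimator. Modified Poisson is still Poisson regression, and the choice of standard error is a normal SAP detail that section 1.26 expressly defers. A reader might infer that the protocol prescribes the default variance and that the adjusted intervals will therefore be wrong. The text does not support that, because it is silent on the estimator and the SAP may name a robust one. This part of the reply stands, and the point is conditional for that reason.

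Three further limits also stand.
- The primary analyses are unadjusted and are not touched.
- For AKI the effect is small, and because it is conservative it creates no false positive findings.
- The large effects rest on complication rates from a 60-patient liver-resection trial. The present cohort is any surgery over two hours with an overnight stay. The protocol gives no complication rate for it and does not say that complications form a single yes/no variable.

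What does not stand is that nothing needs changing. The protocol did not leave the model open. It fixed the family in two places, listed the covariates, and gave a detailed fallback for non-normal continuous outcomes. Having chosen a count model for binary data, it omits the one condition that makes that model's inference valid. An SAP that merely repeated the wording would carry the gap forward.

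**Conclusion.** The point holds in conditional form. As worded, the protocol permits an adjusted analysis whose standard errors are too large by about 1/sqrt(1-p). If the model-based variance is used, the SE excess is about 6% for AKI at the planning rates, about 1% for an outcome at an assumed 2%, and 12% to 51% at risks of 20% to 56%.

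The algebra is certain. Whether the sponsor would use that variance is not known, and neither is the frequency of complications in this cohort. The practical weight therefore lies with common yes/no outcomes, not with AKI. The consequence would be lost precision, and adjusted intervals that cannot be set beside the unadjusted ones. It would not be a spurious association, and the primary result is not at risk.

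**What to change.** In section 1.26 and in the Statistical Methods row of the synopsis, replace the bare reference to Poisson regression for adjusted binary outcomes with: *modified Poisson regression (log link) with robust (sandwich) standard errors*. Carry the same phrase into the SAP. If the SAP already says this, only the two protocol passages need aligning.

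The cost is one phrase and one software option. It needs no extra data, no extra patients and no change to the primary analysis.

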1.15 Baseline data

The following baseline data will be collected:

- Age

FLUid intervention and **Renal Outcome Trial** in patients undergoing major surgery: an observational single-centred study (**FLURO TRIAL**). Version 2, 31st Mar 2014

- Gender
- Admission type (elective vs. emergency)
- Type of surgery (hepatobiliary, colorectal, upper GI, orthopaedic etc.)
- If admitted to ICU: Chronic APACHE co-morbidities (including long-term dialysis)
- If admitted to ICU: APACHE-III admission diagnosis⁴²
- If admitted to ICU: Illness severity based on the on the APACHE-III risk of death score⁴²
- Baseline creatinine.
- Baseline biochemistry

(Note: - all of these data are routinely collected for quality assurance purposes or as measured as part of usual clinical care)

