1.17.2 Secondary outcome measures

- Serum electrolytes
- Acid base disturbances
- Post-operative complications
- Requirements for ICU
- Requirement for dialysis or hemofiltration
- Duration of ICU stay
- Hospital length of stay

FLUid intervention and **Renal Outcome Trial** in patients undergoing major surgery: an observational single-centred study (**FLURO TRIAL**). Version 2, 31st Mar 2014

ETHICS

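### Creatinine is the only laboratory baseline in the planned adjusted models, so the electrolyte and acid-base outcomes are not adjusted for their own preoperative values, and the protocol does not settle whether electrolytes are analysed as levels or as changes

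*Protocol*

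**What the plan says.** Section 1.15 lists "Baseline biochemistry" among the data collected. Unlike the APACHE items in the same list, it is not restricted to patients admitted to ICU. The analytes are not named, and no preoperative blood gas is mentioned.

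Section 1.17.2 lists "Serum electrolytes" and "Acid base disturbances" as secondary outcomes. The second specific aim under Objectives is "The development of biochemical and acid-base derangements". Section 1.6 words the outcomes as follows: "Secondary outcomes will include delta creatinine (the difference between baseline and peak creatinine), serum electrolyte levels, acid base disturbances". There only creatinine is a difference from baseline. The lay summary, however, describes the electrolyte endpoint as changes in electrolytes.

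Section 1.26 sets the analysis: "The primary analyses will be unadjusted analyses in which binary outcomes will be compared using relative risks", with mean differences and unpaired t-tests for continuous outcomes. Adjusted analyses follow, by Poisson regression for binary "outcomes and linear regression for continuous outcomes". One covariate sentence serves all outcomes: "Baseline covariates will include age, gender, elective vs. emergency surgery, surgical specialty of admission, type of operation, and baseline serum creatinine level". The synopsis repeats it. Both places leave the complete description to a statistical analysis plan.

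**The concern.** Baseline creatinine is the natural covariate for the renal outcomes. For postoperative chloride, potassium, sodium or bicarbonate, the natural covariate is the patient's own preoperative value of that analyte, and the list does not contain it.

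In a randomised trial the omission would mainly cost precision. Here fluid choice is left to the treating clinicians. Table 1 gives Plasmalyte and saline different chloride (98 against 150 meq/L) and potassium (5 against 0 meq/L). It is therefore plausible, though the protocol does not say so, that a preoperative electrolyte result influences the choice. If it does, part of a difference that existed before any fluid was given would enter the estimated fluid association, and the second aim could be answered wrongly. The unclear outcome definition adds to this, because the sign of the bias depends on whether levels or changes are analysed.

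**Working it through.** The protocol gives no figure for these outcomes to reproduce; its only power statement concerns acute kidney injury and is not used here.

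**Inputs.** From the protocol: a total of 400 to 600 patients (section 1.25), and the liver-resection trial summarised under feasibility, with a chloride difference of 1.7 mmol/L (95% CI 0.2 to 3.2) in 60 patients. The counts reported there, 23 patients as 77% and 14 as 47%, imply about 30 per arm (23/0.77 = 29.9; 14/0.47 = 29.8). Assumed, because the documents give no value: rho of 0.3, 0.5 or 0.7; a preoperative chloride gap d of 0, 0.5 or 1 mmol/L; two equal groups; equal SDs before and after surgery.

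**Bias.** Let the postoperative value be Y = a + rho·X + tau·G + error, where X is the preoperative value, G the fluid group and tau the true difference.
- Levels, X omitted: the expected group difference is tau + rho·d.
- Changes (Y - X), X omitted: tau + rho·d - d = tau - (1 - rho)·d.
- X included: tau.

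At rho 0.5 and d = 1 mmol/L the bias is +0.5 mmol/L on levels and -0.5 mmol/L on changes. In a model with the listed covariates, d and rho are what remains after those covariates.

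**Illustrative false-positive rate (levels, unadjusted two-group test, tau = 0).**
- Chloride SD = [(3.2 - 0.2)/2/1.96]/sqrt(2/30) = 2.96 mmol/L.
- Standard error at N = 400, equal split: 2.96·sqrt(4/400) = 0.296.
- d = 0.5, rho 0.5: bias 0.25, z = 0.84; two-sided rejection 13%.
- d = 1, rho 0.5: bias 0.50, z = 1.69; rejection 39%.
- d = 0: rejection 5%.

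| N | d (mmol/L) | rho 0.3 | rho 0.5 | rho 0.7 |
|---|---|---|---|---|
| 400 | 0.5 | 8% | 13% | 22% |
| 400 | 1 | 17% | 39% | 66% |
| 600 | 0.5 | 10% | 18% | 30% |
| 600 | 1 | 24% | 54% | 82% |

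On changes the variance is 2(1 - rho) times that of levels. At rho 0.5 the factor is 1 and the bias has the same size with opposite sign, so the rejection rates are the same.

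**Partial check of an adjusted model.** A simulation used 500 patients in two equal groups, no fluid effect, a baseline gap of 0.2 SD and a creatinine term weakly related to the analyte. It rejected in about 10%, 18% and 35% of runs for rho 0.3, 0.5 and 0.7. With the analyte's own baseline added, the rate was about 4% to 5%. The other five listed covariates were not simulated.

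**Precision.** Relative to a comparison of levels, including X multiplies the standard error by sqrt(1 - rho²): 0.95, 0.87 or 0.71 for rho 0.3, 0.5 or 0.7. This is a reduction of about 5%, 13% or 29%, equivalent to 1.10, 1.33 or 1.96 times the sample size. Relative to changes the factor is sqrt((1 + rho)/2): 0.81, 0.87 or 0.92.

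**The case against.** Several points on the other side have force.

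- A reader might infer that these outcomes are adjusted for creatinine and nothing else. That is wrong: five further covariates are listed. Emergency status, specialty and type of operation may absorb part of any preoperative imbalance.
- A reader might infer that a fluid effect will be falsely reported. The documents do not support that. Neither the gap nor the correlation is given, and section 1.6 records that the anaesthetists regard the three fluids as equally acceptable, which argues against strong selection on electrolytes. A 1 mmol/L gap is about a third of the derived SD, and that SD comes from a liver-resection trial, not from this mixed cohort.
- The tabulated rates are for a two-group test without covariates. They illustrate the mechanism and are not the error rate of the planned regression.
- A reader might assume that raw levels will be analysed. The lay summary's reference to changes leaves this open, and on that reading the bias reverses sign.
- The covariate sentence is not worded as exclusive, and the analysis plan, which is not at hand, may extend it.

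These points limit the size and certainty of the concern but do not remove it. The protocol names its covariates twice and gives no sign of outcome-specific baselines, so this is a choice already stated and not merely a detail deferred. A change score does not cure the problem either, since it leaves a bias of -(1 - rho) times the gap.

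**Conclusion.** The point holds in a limited form. The stated adjusted models contain no preoperative electrolyte or acid-base value, although baseline biochemistry is collected, and the electrolyte outcome is described in two ways. Any bias requires a preoperative difference between fluid groups that remains after the listed covariates; its size and sign depend on that difference, on rho and on the outcome definition. Without such a difference the loss is precision alone. All the figures rest on assumed rho and gap values.

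The point is firm for electrolytes and less certain for acid-base outcomes, because section 1.15 names no baseline blood gas. It does not touch the primary outcome, acute kidney injury, which is itself measured from baseline creatinine. It is a minor improvement, worth making because it costs almost nothing.

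**What to change.** - In section 1.26 and the synopsis, state that for each continuous serum electrolyte outcome the linear regression adds the preoperative value of the same analyte, from the baseline biochemistry, to the listed covariates. State that this estimate, rather than the unadjusted difference, will be used to interpret that outcome.
- For acid-base outcomes do the same with one baseline variable for all patients, for example bicarbonate, where it is part of the baseline biochemistry. Do not mix different variables between patients.
- Describe the electrolyte outcome in one way throughout. With the own baseline in a linear model, levels and changes give the same fluid estimate, but the text should still agree.
- Handle missing baselines by multiple imputation, or by a complete-case analysis with a sensitivity check. A missing-indicator can itself bias a non-randomised comparison.

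The cost is one degree of freedom per model and the handling of some missing baselines. For electrolytes in the baseline biochemistry no new measurements are needed; for acid-base this depends on what that biochemistry contains.
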